9 ASSESSMENT OF INVESTIGATIONAL MEDICINAL PRODUCT

Lipid parameters

Blood sampling to determine lipid parameters (ie, TC, LDL-C, HDL-C, TG, non-HDL-C, Apo B, Apo A-1, ratio Apo B/Apo A-1, Apo C III, LDL particle size and number, and Lp [a]) should be performed in the morning, in fasting condition (at least 10 to 12 hours fast and refrain from smoking). Alcohol consumption within 48 hours and intense physical exercise within 24 hours preceding the blood sampling are discouraged.

TC, HDL-C, TG, Apo B, Apo A-1, Apo C-III and Lp(a) will be directly measured by the Central Laboratory as per the schedule in [Section 1.2](#). LDL-C will be directly measured via beta quantification method by the Central Laboratory as per the schedule in Section 1.2. LDL-C will be calculated using the Friedewald formula at all visits (except Weeks 4 and 32). If TG values exceed 400 mg/dL (4.52 mmol/L) then the central lab will reflexively measure (via the beta quantification method) the LDL-C rather than calculating it. Non-HDL-C will be calculated by subtracting HDL-C from the TC. Ratio Apo B/Apo A-1 will be calculated. Triglyceride rich lipoprotein will be calculated by total cholesterol minus HDL cholesterol minus LDL cholesterol. Detailed procedures of sample preparation, storage and shipment will be described in the specific laboratory manual which will be provided to sites.

All patients will qualify for randomization based on the LDL-C value obtained at Week -3 visit. If the patient is not fasting at this or any other visit requiring fasting, then he/she will be asked to come the day after or as close as possible to this date for the blood sampling.

Communication of lipid results by central lab

The lipid results from blood samples obtained after the randomization visit will not be communicated to the Investigators. However, sites will be notified in the event of a TG level ≥ 500 mg/dL (5.65 mmol/L) obtained any time after randomization (ie, TG alert). Repeat testing should be done as soon as possible after a TG alert. For a confirmed TG alert, please refer to relevant information in [Section 8.8.1](#).

Efficacy endpoints will not be considered as AEs, such as those involving abnormalities in lipid levels, unless meeting the criteria in [Section 10.4](#).

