10 STUDY PROCEDURES

The window period for Week 0 is +3 days. The window period for Weeks 8, 12 and 24 is ± 3 days. The window period for Weeks 4, 20, and 32 is ± 7 days.

For all visits after Day 1/inclusion visit, if one visit date is changed, then the next visit should take place according to the original schedule as outlined in the Study Flow Chart ([Section 1.2](#)).

Blood sampling

All blood sampling, including the blood sampling for determination of lipid parameters (eg, TC, LDL-C, HDL-C, TG, non-HDL-C, Apo A, Apo B, Apo C-III, Lp(a), LDL particle size and number) and also for plasma glucose should be performed in the morning, in fasting condition (ie, overnight, at least 10 to 12 hours fast and refrain from smoking), and before IMP injection for all site visits throughout the study. Alcohol consumption within 48 hours and intense physical exercise within 24 hours preceding the blood sampling are discouraged.

Note: if the patient is not in fasting conditions, the blood sample will not be collected and a new appointment will be given to the patient for the day after (or as close as possible to this date), with instructions to fast (see above conditions).

Laboratory tests

The laboratory data are collected in accordance with the study schedule and the details provided in the Study Flow Chart ([Section 1.2](#)).

- Hematology: all visits except Weeks 4 and 20; may be performed at Week 0 as applicable and based on the clinical discretion of the Investigator
- Chemistry: all visits except Visits 3 and 6; may be performed at Week 0 as applicable and based on the clinical discretion of the Investigator, except for plasma glucose which should be performed at Week 0 for all patients
- HbA1c: screening and Weeks 0, 12, and 24
- Lipid panel: screening and Weeks 0, 8, 12, 20, and 24
- Measured LDL-C via beta quantification: Weeks 0, 12, and 24
- Other lipid assessments (Apo B, Apo A-1, Apo C-III, LDL particle size and number, Lp[a]): Weeks 0, 12, and 24
- Liver panel: all visits except Visits 3 and 6; may be performed at Week 0 as applicable and based on the clinical discretion of the Investigator. In case of total bilirubin values above the normal range, differentiation into conjugated and non-conjugated bilirubin will occur automatically
- Creatine Phosphokinase (CPK): all visits except Visits 3 and 6; may be performed at Week 0 as applicable and based on the clinical discretion of the Investigator.

- Hepatitis B surface antigen: screening only.

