2.1.3 Efficacy endpoints

Efficacy parameters include lipid parameters (ie, calculated LDL-C, measured LDL-C, non-HDL-C, Apo B, TC, Lp(a), TG, HDL-C, TGRL, LDL particle size and number, Apo A-1, Apo C-III, ratio Apo B/Apo A-1, TC/HDL-C). All these parameters are measured or calculated by a Central Laboratory, for both scheduled and unscheduled time points. Calculated LDL-C is obtained using the Friedewald formula (2). Non-HDL-C is calculated by subtracting HDL-C from the TC. Measured LDL-C is obtained via beta quantification method. All measured LDL-C values provided by the Central Laboratory including those done in case of TG values exceeding 400 mg/dL (4.52 mmol/L) will not be used for the analysis of calculated LDL-C endpoints. TGRL will be calculated by total cholesterol minus HDL cholesterol minus measured LDL cholesterol. In cases where the measured LDL-C is missing and the calculated LDL-C is non-missing, the calculated LDL-C will be used for the computation of TGRL. Both fasting and non-fasting measurements will be used for calculation of TGRL.

Unless otherwise specified, all lipid values (scheduled or unscheduled, fasting or not fasting) may be used to provide a value for the primary and secondary efficacy endpoints. All measurements, scheduled or unscheduled, fasting or not fasting, will be assigned to analysis windows defined in Section 2.5.4 in order to provide an assessment for Week 8 to Week 24 time points. For TG, only fasting measurements will be used. Measurements with missing fasting status will be excluded from the analyses.

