2.4.5.2.3 Binary endpoints

Binary secondary efficacy endpoints defined in [Section 2.1.3.2](#) (eg, proportion of patients below a threshold) will be analyzed using logistic regression with treatment group as main effect and corresponding baseline value(s) as covariate, stratified by randomization strata. Missing values will be addressed using a multiple imputation approach (see [Section 2.4.5.1.3](#)). The variables in the multiple imputation model will at least include the same variables as used in the logistic regression model. In the logistic regression model, the analyzed endpoint at time point of interest will be derived from observed and imputed lipid values at this time point. Treatment effects will be compared and the combined odds ratio estimate between the treatment groups, with their

corresponding 95% CIs and p-value will be provided via the SAS MIANALYZE procedure. The analysis will be performed by diabetes type and on the pooled data.

In the data dependent case that the logistic regression method is not applicable (eg, the response rate is zero in 1 treatment arm and thus the maximum likelihood estimate may not exist), the last observation carried forward (LOCF) approach would be used for handling of missing values and an exact conditional logistic regression would be performed to compare treatment effects. The LOCF imputation method will consist of using the last value obtained up to the Week 24 analysis window (or Week 12 as applicable) to impute the missing week 24 value (or Week 12 respectively).

In case of computing issues with exact logistic regression, the baseline level(s) will be entered in the model as a categorical variable(s) using quartiles. Exact odds ratio versus placebo, 95% CI, and p-value will be provided.

2.4.5.2.4 *Summary of results per time point*

Central laboratory values (in conventional (US) and international units), percent change from baseline and/or when appropriate absolute change from baseline (in conventional and international units) in calculated LDL-C, measured LDL-C, HDL-C, fasting TG, non-HDL-C, TC, ratio TC/HDL-C, Lp(a), Apo B, Apo A-1, ratio Apo B/Apo A-1, Apo C-III, TGRL, LDL-C particle size, LDL-C particle number will be provided at each time point for each treatment group in the ITT population using:

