2.4.5.2.5 Sensitivity analysis for the computation of TGRL values

Two sensitivity analyses will be performed to assess the impact of the computation of TGRL values on the effect of treatment:

1. In the first sensitivity computation, TGRL will be computed from measured LDL-C only, not replaced by calculated LDL-C in case of missing value of measured LDL-C.
2. In the second sensitivity computation, TGRL will be computed from fasting samples only, ie, non-fasting samples will be excluded from analysis.

For both sensitivity computations, the percent change from baseline to Weeks 12 and 24 (ITT and on-treatment estimands) will be assessed in the same way than for the main computation of TGRL, using the model described in [Section 2.4.5.2.2](#).

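### At Weeks 8 and 20 almost every TGRL value would be only the Friedewald triglyceride term, set against a mostly measured baseline

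*SAP*

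**What the plan says.** - **Definition (SAP 2.1.3).** "TGRL will be calculated by total cholesterol minus HDL cholesterol minus measured LDL cholesterol".
- **Fallback (SAP 2.1.3).** Where the measured value is missing but a calculated one exists, "the calculated LDL-C will be used for the computation of TGRL". No visit is excluded. The same section obtains calculated LDL-C from the Friedewald formula, and it allows both fasting and non-fasting samples for TGRL but only fasting samples for TG.
- **Sampling (Protocol section 10, Laboratory tests).** "Measured LDL-C via beta quantification: Weeks 0, 12, and 24", against "Lipid panel: screening and Weeks 0, 8, 12, 20, and 24".
- **Reflex testing (Protocol section 9).** When TG exceeds 400 mg/dL, "the central lab will reflexively measure (via the beta quantification method) the LDL-C rather than calculating it". SAP 2.1.3 keeps these reflex values out of the calculated LDL-C endpoints, but not out of TGRL.
- **Endpoints (SAP 2.1.3.2.3).** Percent change in TGRL is an endpoint at Weeks 12 and 24 only, among the other efficacy endpoints.
- **Summaries (SAP 2.4.5.2.4).** Values and changes for a list of lipids ending in "Apo C-III, TGRL, LDL-C particle size, LDL-C particle number will be provided at each time point for each treatment group", with graphs over time and observed-data summaries for all lipids.
- **Sensitivity analysis (SAP 2.4.5.2.5).** For a measured-only computation and a fasting-only computation of TGRL, "the percent change from baseline to Weeks 12 and 24 (ITT and on-treatment estimands) will be assessed".

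**The concern.** The fallback reads as a repair for an occasional lost sample. Set against the sampling schedule, it becomes the standard method at two of the four post-baseline lipid visits. The TGRL profile would run measured (Week 0), formula (Week 8), measured (Week 12), formula (Week 20), measured (Week 24). Any systematic gap between the two methods would appear as a zigzag within each arm, which a reader could take for a time course.

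The substituted value also adds nothing to the triglyceride result from the same sample. The measured-only sensitivity analysis does not reach Weeks 8 and 20, where substitution dominates.

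A second route leads to the endpoints themselves. SAP 2.4.5.2.2 sends TGRL to the multiple imputation model of 2.4.5.1.3, which is written with values at Weeks 8, 12, 20 and 24. If TGRL follows that template, formula values at Weeks 8 and 20 would help to impute Weeks 12 and 24. The SAP does not say whether they do.

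**Working it through.** The documents state no figure for TGRL to reproduce, so the check covers the schedule, the algebra and an illustration of scale.

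**1. Which visits depend on the fallback.** Post-baseline lipid panel: Weeks 8, 12, 20, 24. Scheduled measured LDL-C after baseline: Weeks 12, 24. The difference is Weeks 8 and 20. Both endpoint weeks have scheduled measured LDL-C.

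**2. What the fallback computes.** Assumption: Friedewald in mg/dL is LDL-C = TC - HDL-C - TG/5 (the documents name the formula but do not print it). Then

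TC - HDL-C - (TC - HDL-C - TG/5) = TG/5.

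A numerical check over 10,000 random lipid profiles agreed to within 2e-14. For substituted values, the SAP's TGRL category boundary of 30 mg/dL is therefore its TG boundary of 150 mg/dL under another name (150/5 = 30).

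**3. Whether Weeks 8 and 20 enter the output.** SAP 2.1.3 assigns lipid measurements to windows for Week 8 to Week 24, and 2.4.5.2.4 lists TGRL at each time point. Nothing excludes Weeks 8 and 20. Several other parameters in that list (Apo B, Lp(a), the particle measures) have no scheduled samples at those visits, so their summaries limit themselves. TGRL does not, because the fallback produces a value wherever a lipid panel exists.

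**4. Scale of a method switch.** Let r0 be the ratio of measured TGRL to TG in a patient, assumed constant over time, and c the true proportional change. Baseline is r0 × TG. The follow-up value by formula is 0.2 × TG × (1 + c). The apparent percent change is

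100 × [(0.2/r0) × (1 + c) - 1].

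With c = 0 this is 100 × (0.2/r0 - 1), and a true between-arm difference is multiplied by 0.2/r0:

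| Assumed r0 | Apparent change when nothing changed | A true -10 point arm difference reads as |
|---|---|---|
| 0.15 | +33.3% | -13.3 |
| 0.175 | +14.3% | -11.4 |
| 0.20 | 0.0% | -10.0 |
| 0.225 | -11.1% | -8.9 |
| 0.25 | -20.0% | -8.0 |

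The range of r0 is an assumption; the documents give no such ratio. If the gap is a fixed d mg/dL instead, percent change shifts by 100 × d / baseline TGRL in both arms alike, for example 3.3 points per 1 mg/dL at a baseline of 30 mg/dL (1/30).

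**5. Exceptions at Weeks 8 and 20.** Measured-based values can still arise from reflex tests at TG above 400 mg/dL, and from early end-of-treatment samples (Protocol 10.3.4 and 10.1.2.4) that fall in the SAP 2.5.4 windows (days 43-70 and 127-154). A patient whose baseline also used the fallback has the same quantity at both times. The reflex exception means that the method at these visits depends partly on the TG level itself.

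**The case against.** The case for leaving the SAP alone is substantial. No TGRL endpoint exists at Week 8 or 20, and the secondary objective is also confined to Weeks 12 and 24. TGRL is outside the testing hierarchy, and SAP 2.4.5.3 makes its p-values descriptive. The measured-only analysis is already prespecified at both endpoint weeks. The time-point wording is loose, since it covers parameters that are not sampled at every visit, so the sponsor may never have intended TGRL at Weeks 8 and 20. All of this stands and limits the importance of the point. It does not remove it, because as written the rule generates those values and nothing keeps them out of the tables and graph.

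A reader might go further in four ways that the documents do not support:

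- **Every TGRL value at Weeks 8 and 20 is a formula value.** The exceptions in step 5 of the working show otherwise.
- **The switch would look like a treatment effect.** Both randomised arms follow the same rule at each visit, so a common offset largely cancels. A between-arm distortion needs an offset that varies with lipid levels, as in the ratio illustration, and the documents give no basis for sizing it.
- **The artefact is 10 to 20 points.** That follows from assuming a 3 to 6 mg/dL gap at a baseline of 30 mg/dL (3/30 and 6/30). The gap is not in the documents, its sign is unknown, and 30 mg/dL is a category boundary, not an expected mean.
- **TGRL at Weeks 12 and 24 duplicates the TG endpoint.** Only values with missing measured LDL-C are substituted there, and the TG endpoint excludes non-fasting samples that TGRL accepts.

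**Conclusion.** The point holds as a minor one. An unlimited fallback combined with the measured LDL-C schedule makes almost all TGRL values at Weeks 8 and 20 a rescaled TG, compared with a baseline that is mostly measured. The by-time-point summaries, percent changes and graph therefore mix two quantities. The size and direction of the resulting shift cannot be derived from the documents; the table shows only that both signs are possible under assumed ratios.

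The Week 12 and 24 endpoints are touched in two limited ways: through the few substituted values, which the measured-only sensitivity analysis addresses, and possibly through the imputation model, on which the SAP is silent. A reader might infer that the main and sensitivity computations at Weeks 12 and 24 ought to be exchanged. Both are already planned, so their order is closer to preference than to correction.

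The conclusion assumes the usual TG/5 form of the formula and that SAP 2.4.5.2.4 is applied as written.

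**What to change.** 1. In SAP 2.1.3 and 2.4.5.2.4, restrict TGRL values, percent changes, summaries and graphs to Weeks 0, 12 and 24, and state that the fallback is not applied at Weeks 8 and 20.
2. In SAP 2.4.5.2.2, state which visits enter the TGRL imputation model and keep formula-based Week 8 and 20 TGRL values out of it. TG at those visits can serve as an auxiliary variable, which retains the information that the substituted values would have supplied.
3. Where the fallback is kept at Weeks 12 and 24, use the same LDL-C method at baseline and at follow-up within a patient.

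The cost is a few lines of SAP text and the loss of the Week 8 and 20 TGRL points. The formula-based ones add nothing to TG from the same sample, and the few measured-based ones there come mainly from patients with high TG or early discontinuation. No extra sampling is needed, and the two planned sensitivity analyses stay as they are.

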2.1.3.1 Primary efficacy endpoint(s)

The primary efficacy endpoint is the percent change in calculated LDL-C from baseline to Week 24 in the intent-to-treat (ITT) population. Primary endpoint is defined as: $100 \times (\text{calculated LDL-C value at Week 24} - \text{calculated LDL-C value at baseline}) / \text{calculated LDL-C value at baseline}$.

2.1.3.2 Secondary efficacy endpoint(s)

2.1.3.2.1 Key secondary efficacy endpoints

The key secondary endpoints are:

- Percent change in calculated LDL-C from baseline to Week 24, using all calculated LDL-C values during the efficacy treatment period (see Section 2.1.4, on-treatment estimand);
- Percent change in measured LDL-C from baseline to Week 24 (ITT estimand);
- Percent change in calculated LDL-C from baseline to Week 12 (ITT estimand);
- Percent change in measured LDL-C from baseline to Weeks 12 (ITT estimand);
- Percent change in non-HDL-C from baseline to Week 24 (ITT estimand);
- Percent change in Apo B from baseline to Week 24 (ITT estimand);
- Percent change in TC from baseline to Week 24 (ITT estimand);
- The proportion of patients reaching calculated LDL-C <70 mg/dL at Week 24 (on-treatment estimand);

- The proportion of patients reaching calculated LDL-C <50 mg/dL at Week 24 (on-treatment estimand);
- The proportion of patients reaching non-HDL-C <100 mg/dL at Week 24 (on-treatment estimand);
- The proportion of patients reaching non-HDL-C <80 mg/dL at Week 24 (on-treatment estimand);
- The percent change in Lp(a) from baseline to Week 24 (ITT estimand);
- The percent change in HDL-C from baseline to Week 24 (ITT estimand);
- The percent change in TG from baseline to Week 24 (ITT estimand);
- The percent change in LDL-C particle number from baseline to Week 24 (ITT estimand);
- The percent change in LDL-C particle size from baseline to Week 24 (ITT estimand).

2.1.3.2.2 Diabetes-related endpoints

- Absolute change in HbA1c from baseline to Weeks 12 and 24 (ITT and on-treatment estimands);
- Absolute change in FPG from baseline to Weeks 12 and 24 (ITT and on-treatment estimands);
- Absolute change in total daily insulin dose from baseline to Weeks 12 and 24 (ITT and on-treatment estimands);
- Absolute change in insulin daily dose/kg from baseline to Weeks 12 and 24 (ITT and on-treatment estimands);
- Absolute change in number of glucose-lowering treatments from baseline to Weeks 12 and 24 (ITT and on-treatment estimands).

2.1.3.2.3 Other efficacy endpoints

- Percent change in calculated LDL-C from baseline to Week 12 (on-treatment estimand);
- Percent change in measured LDL-C from baseline to Weeks 12 and 24 (on-treatment estimand);
- Percent change non-HDL, Apo B, TC, Lp(a), HDL-C, and TG from baseline to Weeks 12 (ITT and on-treatment estimands) and Week 24 (on-treatment estimand);
- Proportion of patients reaching calculated LDL-C <50 and also <70 mg/dL at Weeks 12 (ITT and on-treatment estimands) and 24 (ITT estimand);
- Proportion of patients with 50% or greater reduction from baseline in calculated LDL-C at Weeks 12 and 24 (ITT estimand);
- Proportion of patients reaching non-HDL-C <80 mg/dL and also <100 mg/dL at Weeks 12 (ITT and on-treatment estimands) and Week 24 (ITT estimand);
- Proportion of patients reaching Apo B <80 mg/dL at Weeks 12 and 24 (ITT and on-treatment estimands);
- Percent change in LDL-C particle number from baseline to Week 12 (ITT and on-treatment estimands) and Week 24 (on-treatment estimand);

- Percent change in LDL-C particle size from baseline to Week 12 (ITT and on-treatment estimands) and Week 24 (on-treatment estimand);
- Percent change in TGRL, Apo A-1, and Apo C-III from baseline to Weeks 12 and 24 (ITT and on-treatment estimands);
- Absolute change in ratio Apo B/Apo A-1 and TC/HDL-C from baseline to Weeks 12 and 24 (ITT and on-treatment estimands);
- Proportion of patients reaching calculated LDL-C <70 and <50 mg/dL at Weeks 12 and 24 according to baseline A1c of <8% or ≥8% (ITT and on-treatment estimands);
- Proportion of patients reaching calculated LDL-C <70 mg/dL and <50 mg/dL at Weeks 12 and 24 according to baseline A1c <median A1c or ≥median A1c (ITT and on-treatment estimands).

2.1.4 Safety endpoints

The safety analysis will be based on the reported AEs and other safety information, such as clinical laboratory data and vital signs.

Observation period

The observation period will be divided into 3 periods:

- Pre-treatment period is defined from the signed informed consent up to the first dose of double-blind IMP injection.
- Treatment Emergent Adverse Event (TEAE) period is defined as the time from the first dose of double-blind IMP injection to the last dose of IMP injection + 70 days (10 weeks) as residual effect of treatment is expected until 10 weeks after the stop of double-blind IMP. As the hour of IMP injection is not collected, the time of double blind IMP injection refers, here and in the rest of the document, to the date of double-blind IMP injection.

The TEAE period will include:

- The efficacy treatment period defined as the time from the first dose of double-blind IMP injection up to the day of last dose of double-blind IMP injection + 21 days, as serum concentration of alirocumab >10 µg/mL is expected for approximately 21 days following administration of 150 mg, and because throughout the previous studies it was observed that when alirocumab concentrations declined below this concentration, decrease in effect on LDL-C is observed.
- The residual efficacy treatment defined as the time from the day of last dose of double-blind IMP injection + 22 days up to the day of last dose of double-blind IMP injection + 70 days (10 weeks).
- Post-treatment period is defined as the time starting the day after the end of the TEAE period up to resolution/stabilization of all serious adverse events (SAE) and AEs of special interest (AESI), whichever comes last.

The on-study observation period is defined as the time from the day of the first dose of double-blind IMP injection until the last protocol planned visit of the patient (Week 32 phone call).

